8 RESEARCH METHODS

8.1 Study Design

The UNITY Global Registry is designed as a comparative cohort study using longitudinal serial surveys implemented through a web/mobile application-based technology to encourage participation and facilitate rapid responses during this pandemic. The study population comprises adult male and female HCWs working in healthcare facilities (e.g., acute care hospital) or in a community healthcare setting (e.g., clinic) with ongoing and continuous exposure to confirmed or clinically diagnosed COVID-19 patients. Countries and healthcare facilities will be selected based on the availability of potential prophylactic treatments to prevent workplace infection from SARS-CoV-2. The association of potential prophylactic treatments will be measured using the WHO Ordinal Scale of Clinical Improvement.⁹

Individuals with workplace exposure to confirmed or clinically diagnosed COVID-19 patients prior to enrollment, or anticipated within 30 days after enrollment, will be eligible to participate. COVID-19 exposure is defined as per WHO classification.⁹ The date of the HCW's first known exposure to a confirmed or clinically diagnosed case of COVID-19 is referred to as the "Index Date" (see Figure 2). Healthcare worker volunteers are ineligible if they had COVID-19 or symptoms highly suggestive of COVID-19 before the Index Date. However, at the time of enrollment, HCWs can be either SARS-CoV-2 positive (symptomatic or asymptomatic) or SARS-CoV-2 negative.

Healthcare workers will be identified for participation via a central contact at participating healthcare facilities and directed to a website/mobile application allowing them to electronically consent (in parallel, paper consents may be used, as per local requirements) and answer questions that would help assess their eligibility to participate. Information on potential prophylactic treatments used by HCWs will also be collected. The website/mobile application will prompt participants to provide entry-level information such as, demographics, underlying conditions, and exposure to COVID-19 patients.

[figure not shown]
Healthcare workers will be expected to provide information on a weekly basis, for 12 weeks after enrollment. In case HCWs stop responding (after due diligence reminders), their secondary contacts (identified by the HCW, may be next of kin or other individuals informed of HCW's health status) will be approached. In case of conflicts, responses by HCWs will take precedence.

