Enrollment will be monitored and potentially capped to ensure that the study enrolls an aggregate of at least 75% of HCWs who are taking a potential prophylactic therapy.

For details on the information collected and the overall study design, refer to [Table 1](#), [Table 2](#), [Figure 1](#), and [Figure 2](#), respectively.

This is a comparative observational cohort study; therefore, no preventive interventions, visits or laboratory tests are mandated. Dosing and duration of potential prophylactic treatment is at the discretion of the institution and/or healthcare provider, in accordance with regular local practice. However, serology testing for SARS-CoV-2 antibodies may be offered to approximately 50% of participating HCWs per country, at enrollment (ranging from baseline up to Week 4 [African countries] and Week 8 [Pakistan]) and at the last follow-up (i.e. at Week 12).

Figure 1 Study Schematic - High-level

HCW: Healthcare Worker

Figure 2 Study Schematic – Healthcare Worker Flow

[figure not shown]

Table 1 Schedule of Assessments – Healthcare Worker Flow

Variable domain	At Enrollment		Weekly follow-up (until Week 12) ^c	
	HCW	HCW	Secondary Contact	
Inclusion/eligibility criteria (screening questions/index date)	X	-	-	-
Electronic/paper (if applicable) consent	X	-	-	-
Demographics	X	-	-	-
Underlying conditions	X	-	-	-
Job characteristics	X	-	-	-
BCG vaccination history	X	-	-	-
Household history (COVID-19)	X	X	-	-
COVID-19 exposure	X	X	-	-
Prophylactic treatments	X	X	-	-
Concomitant medications	X	X	-	-
COVID-19 vaccination ^e	X	X	-	-
PPE	X	X	-	-
COVID-19 symptoms	X	X	-	-
SARS-CoV-2 testing	X	X	-	-
Serology testing ^f	X	X ^b	-	-
WHO Ordinal Scale for Clinical Improvement ^d	X	X	-	X ^a

BCG: Bacillus Calmette–Guérin; CoV: Coronavirus; HCW: Healthcare worker; PPE: Personal Protective Equipment; SARS: Severe acute respiratory syndrome; WHO: World Health Organization.

^a: In case HCWs stop responding (after due diligence reminders), their secondary contacts will be approached. In case of conflicts, responses by HCWs will be considered.

^b: Testing to be requested at last (Week 12) follow-up.

^c: Or, time since last follow-up, whichever is greater.

^d: Adapted, abbreviated version.

^e: From the time the questions on vaccination go live in the web application online survey, baseline vaccination information will only be collected for newly enrolled HCW and for HCWs who did not complete the survey prior to the addition of vaccination questions.

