8.3 Variables

The sections below include outcomes, treatment exposure and PPE use, COVID-19 exposure, COVID-19 vaccinations, and other variables to be measured and accounted for in the study analyses. Refer to [Appendix 2](#) for further details.

8.3.1 *Clinical Outcomes Variables*

- WHO Ordinal Scale for Clinical Improvement of COVID-19 (adapted, abbreviated version)
 - SARS-CoV-2 (uninfected/infected)
 - Ambulatory status (limitation/no limitation of activities)
 - Hospitalized with no intensive care unit (ICU) or mechanical ventilation (mild)
 - Hospitalized with ICU and/or mechanical ventilation (severe)
 - Death

8.3.2 *Prophylactic Treatment (Treatment Exposure)*

- Types, intake frequency, and doses of prophylactic treatments
 - Treatment name
 - Date started
 - Date stopped
 - Dose (intake)
 - Duration of treatment
 - Dose frequency and dosing interval
 - Status (stopped/ongoing)
 - Reason for stopping (not available/side effects/expense/other)
 - Number of missed doses and reason (not available/side effects/expense/other)

8.3.3 *History of Exposure to COVID-19 Patients*

- At enrollment
 - Self-reported ongoing and recurrent exposure (yes/no)
 - WHO exposure definition (3 questions) (yes/no)
 - Direct patient care (yes/no)
 - Face-to-face contact (yes/no)
 - Present during aerosol-generating procedure (yes/no)
- Weekly follow-up
 - Self-reported ongoing and recurrent exposure (yes/no)
 - WHO exposure definition (3 questions) for past week

- Days worked past week
- Number of COVID-19 cases exposed to in the past week

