8.8 Quality Control

8.8.1 Data Quality Assurance

The participants themselves will directly enter all study data on electronic web data entry form in a secure registry system. To the best of the Sponsor's ability, data logic and validation checks will be configured in the platform so that participants will receive warning messages at time of entry of inconsistent or invalid entries, in order to ensure quality and completeness of data.

After verification of eligibility and study enrollment, the self-reported data will not be queried for clarification or correction by the Sponsor after a participant's submission of the electronic web data form into the registry.

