Appendix 2: Detailed SoA

Variable domain	At Enrollment	Weekly follow-up (until Week 12)	
		HCW	HCW Contact
Inclusion/eligibility criteria			
Screening questions	X	-	-
Index date (date of first COVID-19 exposure)	X	X	-
Electronic/Paper (if applicable) consent			
	X	-	-
Demographics			
Contact information	X	-	-
Secondary contact	X	-	-
Facility	X	-	-
Date of birth (Age)	X	-	-
Gender	X	-	-
Weight	X	-	-
Height	X	-	-
Race	X	-	-
Blood type	X	-	-
Smoking status (current/past/never smoked)	X	-	-
BCG vaccination history (date, time period)	X	-	-
WHO Ordinal Scale for Clinical Improvement of COVID-19 (adapted, abbreviated version)			
SARS-CoV-2 (uninfected/ infected)	X	X	X
Ambulatory status (limitation/no limitation of activities)	X	X	X
Hospitalized with no ICU or mechanical ventilation (mild)	X	X	X
Hospitalized with ICU or mechanical ventilation (severe)	X	X	X
Death	-	-	X
Prophylactic treatments (treatment exposure)			
Treatment name	X	X	-
Date started	X	X	-
Date stopped	X	X	-
Dose (intake)	X	X	-
Duration of treatment	X	X	-
Dose frequency and dosing interval	X	X	-
Status (stopped/ongoing)	X	X	-
Reason for stopping (not available/side effects/ expense/other)	X	X	-
Number of missed doses (yes/no)	X	X	-
If yes, reason? (not available/side effects/expense/other)	X	X	-
History of exposure to COVID-19 patients			
Self-reported ongoing and recurrent exposure (yes/no)	X	X	-
WHO exposure definition (3 questions) (yes/no)	X	X	-
Direct care to COVID-19 patient (yes/no)	X	X	-
Face-to-face contact (yes/no)	X	X	-
Present during aerosol-generating procedures (yes/no)	X	X	-
Days worked past week	-	X	-
Number of COVID-19 cases exposed to in the past week	-	X	-
Personal Protective Equipment			
Mask (N95 respirator mask or other) (if yes, always/not always)	X	X	-
Eye protection/goggles/face shield (if yes, always/not always)	X	X	-
Gown (if yes, always/not always)	X	X	-
Gloves (if yes, always/not always)	X	X	-
If “not always” or “no” for mask:			

Number of COVID-19 cases exposed to in the absence of a mask in the prior week	-	X	-
Longest COVID-19 exposure in the absence of a mask	-	X	-
COVID-19 symptoms			
Develop symptoms (yes/no), if yes – date the symptoms begin:	X	X	-
Fever (temperature over 38°C)	X	X	-
Subjective fever (felt feverish)	X	X	-
Chills	X	X	-
Myalgia (muscles hurt or ache)	X	X	-
Rhinorrhea (runny or drippy nose)	X	X	-
Pharyngitis (sore throat)	X	X	-
Cough (new onset or worsening of chronic cough)	X	X	-
Dyspnea (hard to breathe or difficulty breathing)	X	X	-

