Pneumonia	X	X	-
Nausea or vomiting	X	X	-
Headache or migraine	X	X	-
Abdominal pain (pain in tummy)	X	X	-
Asthenia (weakness or loss of strength)	X	X	-
Arthralgia (joint pain)	X	X	-
Anosmia (loss of smell)	X	X	-
Ageusia (loss of taste)	X	X	-
Blue coloring in toes	X	X	-
Diarrhea (two or more looser-than-normal stools in 24 hours)	X	X	-
SARS-CoV-2 testing			
Tested? (yes/no)	X	X	-
Type of test	X	X	-
PCR (positive/negative)	X	X	-
Antigen test (positive/negative)	X	X	-
Serology (IgG and/ or IgM, positive/negative or titer)	X	X	-
Date of test	X	X	-
Serology testing	X	X	-
Household history (COVID-19)			
Number of household contacts	X	X	-
Additional household member(s) exposed to COVID-19 (yes/no) If yes, how many?	X	X	-
Additional household member(s) with symptoms consistent with COVID-19 (yes/no) If yes, how many?	X	X	-
Additional household member(s) diagnosed with COVID-19 (yes/no) If yes, how many?	X	X	-
Underlying conditions and key morbidities			
Chronic lung disease	X	-	-
Diabetes mellitus	X	-	-
Cardiovascular (heart) disease	X	-	-
Chronic renal (kidney) disease	X	-	-
Chronic liver disease	X	-	-
Immunocompromised condition (HIV/AIDS, organ transplant, other)	X	-	-
Tuberculosis	X	-	-
Neurologic/neurodevelopmental	X	-	-
Hypertension (high blood pressure)	X	-	-
History of stroke	X	-	-
Other chronic diseases	X	-	-
If female, currently pregnant	X	-	-
If female, currently breastfeeding/lactating	X	-	-
Job characteristics			
Type of healthcare work	X	-	-

Primary work location (ED, ICU, Medical floor)	X	X	-
Number of hours with patients	X	X	-
Concomitant medications (other than for COVID-19)			
Antibiotics (yes/no)	X	X	-
Antimalarials (yes/no)	X	X	-
Antiparasitics (yes/no)	X	X	-
Antiretrovirals for HIV (yes/no)	X	X	-
Antivirals (yes/no)	X	X	-
Medication for high blood pressure and cardiovascular disease (yes/no)	X	X	-
Nonsteroidal Anti-inflammatory Drugs (NSAIDs) (yes/no)	X	X	-
Botanicals (yes/no)	X	X	-
Immunocompromising drugs (yes/no)	X	X	-
COVID-19 vaccine (to be selected as applicable)			
Convidicea (Ad5-nCoV)	X	X	
CoronaVac (Sinovac)	X	X	
Covaxin (BBV152)	X	X	
EpiVacCorona (Vector Institute)	X	X	
Janssen Pharmaceuticals (Johnson & Johnson) (Ad26.COV2.S)	X	X	
Moderna COVID-19 Vaccine	X	X	
Novavax (NVX-CoV2373)	X	X	
Oxford-AstraZeneca COVID-19 Vaccine	X	X	
Pfizer-BioNTech COVID-19 Vaccine	X	X	
Sinopharm BBIBP-CorV	X	X	
Sputnik V COVID-19 Vaccine	X	X	
Other (please specify)	X	X	

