6.1 Overview.....	17
6.2 Missing values.....	18
6.2.1 Missing values for non-outcome variables	18
6.2.2 Missing values for outcomes.....	18
6.3 Descriptive analyses.....	18

6.3.1	Facility characteristics.....	19
6.3.2	Demographic characteristics.....	19
6.3.3	Household characteristics.....	20
6.3.4	Exposure to COVID-19 patients.....	20
6.3.5	Medical history.....	21
6.3.6	Medications for non-COVID-19 related purposes.....	22
6.3.7	Prophylactic medications.....	23
6.3.8	PPE usage	24
6.3.9	COVID-19 symptoms.....	25
6.4	Primary analysis	26
6.4.1	Frailty model: mixed effect Cox regression	26
	Table 5.4.1.....	26
6.5	Secondary analysis	27
6.6	Subgroup analyses	28
6.7	Sensitivity analyses	28
7	Minimization of study bias.....	30
7.1	Selection bias	30
7.2	Survival bias	30
7.3	Recall bias.....	30
7.4	Information bias.....	30
7.5	Indication bias.....	30
7.6	Protopathic bias	31
8	References	31
9	Appendix.....	32
9.1	Shell tables.....	33
	Table 8.2.1 COVID-19 exposure status among all screened healthcare workers.....	33
	Table 8.2.2 Primary and Secondary Outcomes at baseline and follow-up among the overall population	34
Table 8.2.3	Static Variables by COVID-19 indication	35
Table 8.2.4	Household characteristics at baseline by COVID-19 indication.....	37
Table 8.2.5	COVID-19 exposure at baseline by COVID-19 indication	39
Table 8.2.6	Comorbidities at baseline by COVID-19 indication.....	40

Table 8.2.7 Concomitant medications at baseline by COVID-19 indication.....	41
Table 8.2.8 Prophylaxis use.....	43
Table 8.2.9 PPE usage at baseline.....	44

1 Introduction

The purpose of this statistical analysis plan (SAP) is to provide an analytic framework for the study “International Registry of Healthcare Workers Exposed to COVID-19 Patients (UNITY Global)”. This SAP addresses the statistical analyses that will be carried out in support of the protocol objectives. This analysis plan is based on the protocol version 1.0 of the study dated 08 June 2020.

2 Objectives of the study

This is an international registry of HCWs exposed to SARS-CoV-2 while caring for confirmed or clinically diagnosed COVID-19 patients. The aim of this registry is to generate real-world evidence in HCWs to potentially inform recommendations and policies on prevention measures, including prophylactic use of potential drug therapies in HCWs.

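### COVID-19 vaccination is specified as a product list without dose dates or counts, and workers who completed the survey before go-live get no baseline question, so it cannot be adjusted for correctly over time.

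*Protocol*

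**What the plan says.** Protocol 8.3 names "COVID-19 vaccinations, and other variables to be measured and accounted for in the study analyses" and sends the reader to Appendix 2 for detail. The Appendix 2 block is titled "COVID-19 vaccine (to be selected as applicable" and holds eleven named products plus Other; the list in 8.3.5 is the same. Neither has a dose date, a number of doses, or an explicit item for not vaccinated.

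The Table 1 row "COVID-19 vaccination ^e" is marked both at enrolment and at the worker's weekly follow-up. Its footnote limits the enrolment part: "baseline vaccination information will only be collected for newly enrolled HCW and for HCWs who did not complete the survey prior to the addition" of the vaccination questions. Follow-up is short: "Healthcare workers will be expected to provide information on a weekly basis, for 12 weeks after enrollment". Protocol 8.8.1 adds that, once a form is submitted, "the self-reported data will not be queried for clarification or correction by the Sponsor".

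The SAP predates the vaccination amendment: "This analysis plan is based on the protocol version 1.0 of the study dated 08 June 2020". Vaccination against COVID-19 appears in none of its variable lists (3.6), propensity-score covariates (6.3), model covariates (Table 5.4.1) or shell tables (9.1).

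**The concern.** A COVID-19 vaccine probably affects the primary outcome, and its uptake may well differ between workers who take prophylaxis and those who do not. Vaccination is therefore a likely confounder of the prophylaxis hazard ratio, and one that changes during the period analysed. Adjusting for it requires knowing when each worker moved from unvaccinated to vaccinated.

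A product name without a date does not supply that. In addition, part of the cohort is not asked about baseline status at all, and that part is defined by calendar period of enrolment. Adding a vaccination term to the SAP would then leave some confounding in place and could credit a vaccine with follow-up time, or an infection, that came before the dose. Each worker leaves the registry after at most 12 weeks, so the opportunity to ask is lost worker by worker.

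**Working it through.** **1. The plan's own effect size, used as a yardstick.** Protocol 8.7.7 and SAP 5 give N = 10,000, 20% unexposed, 10% baseline risk, and 80% power at RR 0.78. Expected events are 2,000 × 0.10 + 8,000 × 0.078 = 824. Treating the RR as an HR, the Schoenfeld formula with a two-sided 5% test gives 81.4% power, so the stated figure reproduces. On the log scale the design effect is ln 0.78 = −0.248.

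**2. What is dated and what is not.** Appendix 2 asks for "BCG vaccination history (date, time period" under BCG. It asks for start and stop dates for each prophylactic drug, a test date, and a symptom onset date. The COVID-19 vaccine block has no date.

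**3. Who supplies what, reading the survey in footnote e as the baseline survey.**

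| Group at go-live | Baseline product | Weekly product | Timing of earlier doses |
|---|---|---|---|
| Enrols after go-live | Yes | Yes | Not specified |
| Enrolled, survey not yet completed | Yes (footnote e) | Yes | Not specified |
| Survey completed, still in follow-up | No | Yes, from go-live | Depends on the weekly wording, which is not given |
| Finished follow-up | No | No | None |

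The last two groups are likely to exist. Amendment 1 is dated 11 June 2021, a year after protocol 1.0, and its rationale describes in the past tense how workers were offered serology. Their size is not stated, nor is the go-live date.

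**4. Why the date matters.** SAP 6.4.1 starts the clock at first known exposure for controls and 7 days after treatment start for prophylaxis users. Either can precede enrolment: SAP 6.6 foresees gaps from index date to enrolment of more than 3 months, and Protocol 8.1 admits workers already infected at enrolment. A product ticked at enrolment may therefore have been given before time zero, between time zero and drug start, or after infection. The listed items do not separate these cases.

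**5. Size of the confounding, on assumed inputs.** Let v be the vaccine HR, and a and b the vaccinated shares among prophylaxis users and non-users. None of these is in the documents. With vaccination wholly uncaptured, the prophylaxis HR is multiplied by

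(1 − (1 − v)a) / (1 − (1 − v)b).

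- a = 0.2, b = 0.4, v = 0.5: 0.90/0.80 = 1.125
- a = 0.2, b = 0.4, v = 0.3: 0.86/0.72 = 1.194
- shares reversed: 0.80/0.90 = 0.889 and 0.72/0.86 = 0.837

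Against the design effect, ln 1.125 / 0.248 = 0.47 and ln 1.194 / 0.248 = 0.72.

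**6. Only part of the cohort is affected.** If a fraction f lacks usable status and the rest is properly adjusted, the factor shrinks roughly to its f-th power:

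- f = 0.25: 1.125^0.25 = 1.03; 1.194^0.25 = 1.05
- f = 0.50: 1.125^0.5 = 1.06; 1.194^0.5 = 1.09

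The documents do not allow f to be estimated.

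**The case against.** Several stronger readings are tempting and do not hold.

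- *No one enrolled before go-live has vaccination data.* Footnote e expressly includes workers who had not completed the survey, and Table 1 and Appendix 2 also collect vaccination weekly. Footnote c widens the weekly report to the time since the last follow-up, so a worker active at go-live can report a product dated to about that interval. If the survey in footnote e means the whole series rather than the baseline form, active workers would be asked for baseline status too. Complete absence is certain only for those who had finished.
- *The survey collects brand and nothing else.* The survey screens are not in the documents, and Appendix 2 is not a full item list: the SAP reports cancer, obesity and average weekly patient contacts over the past month, none of which Appendix 2 contains. What can be said is that no dose date or count is specified. If date fields exist, stating them closes that part; the baseline gap remains.
- *Early enrollees will be coded as unvaccinated or dropped.* No document says so. SAP 6.2.1 describes missing and not-known values and leaves multiple imputation open; complete-case analysis is mentioned only under outcomes. With no vaccination variable in the SAP, there is no coding rule.
- *The expected bias is 1.13 to 1.19.* That range assumes status is captured for nobody, which is the effect of leaving vaccination out of the model altogether. It is a ceiling for the data-collection gap.

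It is also fair to say that the missing SAP term comes first: until it is added, dose dates change no planned analysis. But the term cannot work properly without dated data, and the data can be collected only while workers are in follow-up.

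**Conclusion.** The point holds in a limited form. The protocol commits the study to accounting for COVID-19 vaccination, but the items it specifies cannot place a dose in time, and its collection rule leaves baseline status unasked for workers who completed the survey before go-live. Workers who finished before then have no vaccination data; for those still active, capture of earlier doses is not stated. Vaccination therefore cannot be modelled correctly as a time-varying confounder, and the SAP as written does not model it at all.

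The multiplier is at most 1.13 to 1.19 (0.84 to 0.89 if coverage is reversed) under the assumed vaccine HR and coverage, and about 1.03 to 1.09 if a quarter to a half of the cohort is affected. The direction is unknown. These figures rest on assumed inputs and an approximate scaling. They show that the gap is worth closing, not what the bias will be.

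**What to change.** In the protocol, amend footnote e and Appendix 2 as follows:

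- At the next weekly survey, ask every worker still in follow-up once for all COVID-19 vaccine doses ever received, with the product and date of each and an explicit option for none.
- Ask new workers the same at enrolment.
- Record new doses weekly with their dates.

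This is a new question and not a query on submitted data, so it does not conflict with 8.8.1. If the screens already hold these fields, state them in Appendix 2.

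In the SAP, update the basis to protocol 1.1. Add vaccination as a time-varying covariate from the dose date, kept in the model regardless of its p-value, as facility and country already are. Report how many workers have unknown status, by prophylaxis group. Add a sensitivity analysis limited to workers with known, dated status. A separate level for workers who were not asked is not enough on its own: it does not remove confounding within that level, and it tracks enrolment period.

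The cost is a small survey burden and an amendment line. Workers who have already finished cannot be recovered, and the known-status subset will lean towards later enrollees, which the report should say.

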8.1.1 Primary Outcome

- Occurrence of SARS-CoV-2 infection among HCWs caring for COVID-19 patients, in terms of time, geography, healthcare setting, type of HCW.

8.1.2 Secondary Outcomes

- Occurrence of SARS-CoV-2 uninfected HCWs.
- Occurrence of SARS-CoV-2 infection with ambulatory status and no limitation of activities.
- Occurrence of SARS-CoV-2 infection with ambulatory status and limitation of activities.
- Occurrence of hospitalization due to COVID-19 illness with mild disease.
- Occurrence of hospitalization due to COVID-19 illness with severe disease.
- Occurrence of all-cause mortality.
- Type of prophylactic treatments by dose, frequency and duration, overall and by country/region/site.

